Appendix 3: SARS-CoV-2 Infection SYMPTOM CHECKLIST

Please read the below question and check one box that describes your symptoms of the following SARS-CoV-2 infection symptoms.

		Absent (0)	Mild (1)	Moderate (2)	Severe (3)
1	Feeling feverish				
2	Cough				
3	Shortness of breath or difficulty breathing				
4	Sore throat				
5	Body pain or muscle pain				
6	Fatigue				
7	Headache				

Appendix 4: CTCAE v5.0 for Clinical Laboratory Test Results

CTCAE Term	Laboratory Parameter	Level	Grade 1	Grade 2	Grade 3	Grade 4
Alanine aminotransferase increased	Alanine Aminotransferase (ALT)	High	>ULN - 3.0 x ULN if baseline was normal; 1.5 - 3.0 x baseline if baseline was abnormal	>3.0 - 5.0 x ULN if baseline was normal; >3.0 - 5.0 x baseline if baseline was abnormal	>5.0 - 20.0 x ULN if baseline was normal; >5.0 - 20.0 x baseline if baseline was abnormal	>20.0 x ULN if baseline was normal; >20.0 x baseline if baseline was abnormal
Hypoalbuminemia	Albumin	Low	<LLN - 3 g/dL; <LLN - 30 g/L	<3 - 2 g/dL; <30 - 20 g/L	<2 g/dL; <20 g/L	-
Alkaline phosphatase increased	Alkaline phosphatase (ALP)	High	>ULN - 2.5 x ULN if baseline was normal; 2.0 - 2.5 x baseline if baseline was abnormal	>2.5 - 5.0 x ULN if baseline was normal; >2.5 - 5.0 x baseline if baseline was abnormal	>5.0 - 20.0 x ULN if baseline was normal; >5.0 - 20.0 x baseline if baseline was abnormal	>20.0 x ULN if baseline was normal; >20.0 x baseline if baseline was abnormal
Aspartate aminotransferase increased	Aspartate Aminotransferase (AST)	High	>ULN - 3.0 x ULN if baseline was normal; 1.5 - 3.0 x baseline if baseline was abnormal	>3.0 - 5.0 x ULN if baseline was normal; >3.0 - 5.0 x baseline if baseline was abnormal	>5.0 - 20.0 x ULN if baseline was normal; >5.0 - 20.0 x baseline if baseline was abnormal	>20.0 x ULN if baseline was normal; >20.0 x baseline if baseline was abnormal
Blood bilirubin increased	Total Bilirubin	High	>ULN - 1.5 x ULN if baseline was normal; > 1.0 - 1.5 x baseline if baseline was abnormal	>1.5 - 3.0 x ULN if baseline was normal; >1.5 - 3.0 x baseline if baseline was abnormal	>3.0 - 10.0 x ULN if baseline was normal; >3.0 - 10.0 x baseline if baseline was abnormal	>10.0 x ULN if baseline was normal; >10.0 x baseline if baseline was abnormal
Leukocytosis	White Blood Cells	High	-	-	>100,000/mm ³	-
White blood cell decreased	White Blood Cells	Low	<LLN - 3000/mm ³ ; <LLN - 3.0 x 10 ⁹ /L	<3000 - 2000/mm ³ ; <3.0 - 2.0 x 10 ⁹ /L	<2000 - 1000/mm ³ ; <2.0 - 1.0 x 10 ⁹ /L	<1000/mm ³ ; <1.0 x 10 ⁹ /L
Creatinine increased ¹⁾	Creatinine	High	>ULN - 1.5 x ULN	>1.5 - 3.0 x baseline; >1.5 - 3.0 x ULN	>3.0 x baseline; >3.0 - 6.0 x ULN	>6.0 x ULN
Eosinophilia	Eosinophils (Absolute Ct)	High	>ULN and >Baseline	-	-	-
GGT increased	Gamma Glutamyl Transferase (GGT)	High	>ULN - 2.5 x ULN if baseline was normal; 2.0 - 2.5 x baseline if	>2.5 - 5.0 x ULN if baseline was normal; >2.5 - 5.0 x baseline	>5.0 - 20.0 x ULN if baseline was normal; >5.0 - 20.0 x baseline	>20.0 x ULN if baseline was normal; >20.0 x baseline if

			baseline was abnormal	if baseline was abnormal	if baseline was abnormal	baseline was abnormal
Hypercalcemia	Calcium	High	Corrected serum calcium of >ULN - 11.5 mg/dL; >ULN - 2.9 mmol/L; @	Corrected serum calcium of >11.5 - 12.5 mg/dL; >2.9 - 3.1 mmol/L; @	Corrected serum calcium of >12.5 - 13.5 mg/dL; >3.1 - 3.4 mmol/L; @	Corrected serum calcium of >13.5 mg/dL; >3.4 mmol/L; @
Hypocalcemia	Calcium	Low	Corrected serum calcium of <LLN - 8.0 mg/dL; <LLN - 2.0 mmol/L; @	Corrected serum calcium of <8.0 - 7.0 mg/dL; <2.0 - 1.75 mmol/L; @	Corrected serum calcium of <7.0 - 6.0 mg/dL; <1.75 - 1.5 mmol/L; @	Corrected serum calcium of <6.0 mg/dL; <1.5 mmol/L; @
Hypoglycemia	Glucose	Low	<LLN - 55 mg/dL; <LLN - 3.0 mmol/L	<55 - 40 mg/dL; <3.0 - 2.2 mmol/L	<40 - 30 mg/dL; <2.2 - 1.7 mmol/L	<30 mg/dL; <1.7 mmol/L
Anemia	Hemoglobin	Low	<LLN - 10.0 g/dL; <LLN - 6.2 mmol/L; <LLN - 100 g/L	<10.0 - 8.0 g/dL; <6.2 - 4.9 mmol/L; <100 - 80 g/L	<8.0 g/dL; <4.9 mmol/L; <80 g/L	-
Hemoglobin increased	Hemoglobin	High	Increase in >0 - 2 g/dL from ULN or above baseline if baseline is above ULN	Increase in >2 - 4 g/dL from ULN or above baseline if baseline is above ULN	Increase in >4 g/dL from ULN or above baseline if baseline is above ULN	-
Blood lactate dehydrogenase increased	Lactate Dehydrogenase (LDH)	High	>ULN	-	-	-
Lymphocyte count decreased	WBC Differential, Lymphocytes	Low	<LLN - 800/mm ³ ; <LLN - 0.8 x 10 ⁹ /L	<800 - 500/mm ³ ; <0.8 - 0.5 x 10 ⁹ /L	<500 - 200/mm ³ ; <0.5 - 0.2 x 10 ⁹ /L	<200/mm ³ ; <0.2 x 10 ⁹ /L
Lymphocyte count increased	WBC Differential, Lymphocytes	High	-	>4000/mm ³ - 20,000/mm ³	>20,000/mm ³	-
Platelet count decreased	Platelet count	Low	<LLN - 75,000/mm ³ ; <LLN - 75.0 x 10 ⁹ /L	<75,000-50,000/mm ³ ; <75.0 - 50.0 x 10 ⁹ /L	<50,000-25,000/mm ³ ; <50.0 - 25.0 x 10 ⁹ /L	<25,000/mm ³ ; <25.0 x 10 ⁹ /L
Hyperkalemia	Potassium	High	>ULN - 5.5 mmol/L	>5.5 - 6.0 mmol/L	>6.0 - 7.0 mmol/L	>7.0 mmol/L
Hypokalemia	Potassium	Low	<LLN - 3.0 mmol/L		<3.0 - 2.5 mmol/L	<2.5 mmol/L
Hypernatremia	Sodium	High	>ULN - 150 mmol/L	>150 - 155 mmol/L	>155 - 160 mmol/L;	>160 mmol/L
Hyponatremia	Sodium	Low	<LLN - 130 mmol/L	125-129 mmol/L	120-124 mmol/L regardless of symptoms	<120 mmol/L

Cholesterol high	Total Cholesterol	High	>ULN - 300 mg/dL; >ULN - 7.75 mmol/L	>300 - 400 mg/dL; >7.75 - 10.34 mmol/L	>400 - 500 mg/dL; >10.34 - 12.92 mmol/L	>500 mg/dL; >12.92 mmol/L
Neutrophil count decreased	WBC Differential, Neutrophils	Low	<LLN - 1500/mm ³ ; <LLN - 1.5 x 10 ⁹ /L	<1500 - 1000/mm ³ ; <1.5 - 1.0 x 10 ⁹ /L	<1000 - 500/mm ³ ; <1.0 - 0.5 x 10 ⁹ /L	<500/mm ³ ; <0.5 x 10 ⁹ /L
Hypertriglyceridemia	Triglyceride	High	150 mg/dL - 300 mg/dL; 1.71 mmol/L - 3.42 mmol/L	>300 mg/dL - 500 mg/dL; >3.42 mmol/L - 5.7 mmol/L	>500 mg/dL - 1000 mg/dL; >5.7 mmol/L - 11.4 mmol/L	>1000 mg/dL; >11.4 mmol/L

LLN = lower limit of normal, ULN = upper limit of normal.

1) The most severe grade is counted if the CTCAE grade is discrepant by multiple definitions.

Note: The LLN and ULN values will be the lower and upper limits of the normal ranges as provided by the local laboratory at each relevant transfer. In case numeric value for grading is identical such as Hypokalemia, CTCAE grade which includes numeric value will only be applied, because abnormal laboratory value with clinical input was reported as an adverse event and graded accordingly. @ indicates that corrected calcium (mg/dL) = measured total calcium (mg/dL) + 0.8 (4.0 – serum albumin [g/dL]), where 4.0 represents the average albumin level. For SI units as: Corrected calcium (mmol/l) = total Ca (mmol/l) + 0.02 (40 –serum albumin [g/l]).

Appendix 5: Tables, Listings and Figures in the Initial Analysis (For first CSR)

Output Number	Title	Analysis set
Listings:		
Listing 16.2.1.1	Patient Disposition	ITT set
Listing 16.2.2.1	Analysis Sets	ITT set
Listing 16.2.2.2	Major Protocol Deviations	ITT set
Listing 16.2.2.3	Screening Failures	
Listing 16.2.4.1	Demographics	ITT set
Listing 16.2.4.4	Medical History	ITT set
Listing 16.2.4.5	Prior Medication	ITT set
Listing 16.2.4.6	Concomitant Medication	ITT set
Listing 16.2.5.1	Study Drug Administration	ITT set
Listing 16.2.6.1	Reverse Transcription Polymerase Chain Reaction (RT-PCR)	ITT set
Listing 16.2.6.2	Viral Shedding in Nasopharyngeal Swab Specimens based on qPCR	ITT set
Listing 16.2.6.7	Individual Serum Concentration of CT-P59 (Unit)	Safety set
Listing 16.2.6.8	Individual Serum Pharmacokinetic Parameters of CT-P59	PK set
Listing 16.2.7.1	Adverse Events	Safety set
Listing 14.3.2.1	Deaths	Safety set
Listing 14.3.2.2	Serious Adverse Events: Additional Information	Safety set
Listing 14.3.2.3	Infusion Related Reaction including hypersensitivity/anaphylactic reactions: Additional Information	Safety set
Listing 16.2.8.1	Clinical Chemistry	Safety set
Listing 16.2.8.2	Hematology	Safety set
Listing 16.2.8.3	Urinalysis	Safety set
Listing 16.2.9.1	Vital Signs and Weight	Safety set
Listing 16.2.9.2	Vital Signs for Hypersensitivity Monitoring	Safety set
Listing 16.2.9.3	Electrocardiograms	Safety set
Listing 16.2.9.4	Physical Examinations	Safety set
Listing 16.2.9.6	Radiography	Safety set

Listing 16.2.9.7	Immunogenicity Results	Safety set
Listing 16.2.9.8	SARS-CoV-2 Infection Related Signs and Symptoms	Safety set
Listing 16.2.9.9	Antibody-dependent Enhancement	Safety set
Tables:		
Table 14.1.1	Summary of Patient Disposition	ITT set
Table 14.1.2	Analysis Sets	ITT set
Table 14.1.3	Summary of Demographics	ITT set
Table 14.1.7	Study Drug Administration	Safety set
Table 14.2.1.1	Summary of Viral Shedding in Nasopharyngeal Swab Specimens (qPCR)	ITT set
Table 14.2.1.7	Actual Result and Change from Baseline for Viral Shedding in Nasopharyngeal Swab Specimens (qPCR)	ITT set
Table 14.2.3.1	Summary of Serum Concentration of CT-P59 (Unit)	PK set
Table 14.2.3.2	Summary of Serum Pharmacokinetic Parameters of CT-P59	PK set
Table 14.2.3.3	Statistical Analysis to Assess Dose Proportionality	PK set
Table 14.3.1.1	Treatment-Emergent Adverse Events by Intensity	Safety set
Table 14.3.1.2	Treatment-Emergent Serious Adverse Events by Intensity	Safety set
Table 14.3.1.4	Treatment-Emergent Adverse Events classified as Infusion related reaction including hypersensitivity/anaphylactic reactions	Safety set
Table 14.3.1.5	Signs and Symptoms of Treatment-Emergent Adverse Events Classified as Infusion Related Reaction including hypersensitivity/anaphylactic reactions	Safety set
Table 14.3.6.7	Summary of Immunogenicity	Safety set
Table 14.3.6.10	Proportion of patients with Suspicious Antibody-dependent Enhancement	ITT set
Figures:		
Figure 14.2.2.1	Mean (+/- SD) Serum Concentration of (unit)	PK set
Figure 14.2.2.2	Individual Serum Concentration of (unit)	PK set
Figure 14.2.2.3	Scatter plot of PK Parameter versus Dose	PK set
Figure 14.2.3.1	Mean (+/-SD) Viral Titer (log values) from qPCR	ITT set

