## **2.2 Study Endpoints**

### **2.2.1 Primary Endpoints**

Primary endpoints will be analyzed based on the data up to Day 14 of the last enrolled patient.

- Treatment-emergent adverse events (TEAEs)
- Treatment-emergent serious AEs (TESAEs)
- Treatment-emergent AEs of special interest (TEAESI; infusion related reactions including hypersensitivity/anaphylactic reaction)
- Potential effects on the incidence of antibody-dependent enhancement (ADE)
- Vital signs (blood pressure, heart rate, body temperature, SpO2 and respiratory rate)
- Hypersensitivity monitoring
- Twelve-lead electrocardiogram (ECG)
- Severe Acute Respiratory Syndrome Coronavirus infection related signs and symptoms
- Radiography (chest x-ray and/or chest CT)
- Clinical laboratory test (clinical chemistry, hematology, and urinalysis)

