### 7.4.3 Safety Analysis

Safety analyses will be performed in the Safety Set, unless otherwise indicated.

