#### **7.4.3.8 Potential Effects on the Incidence of Antibody-dependent Enhancement**

The number and percentage of patients with suspicious ADE will be presented by the cohort of CT-P59 groups and pooling of placebo group.

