5.4. Analysis sets

Analysis sets and its definitions are described in this section. The analysis set will be identified and included as a subtitle of each TLF.

The following treatment groups will be used for analysis: CT-P59 20 mg/kg, CT-P59 40 mg/kg, CT-P59 80 mg/kg and placebo. For placebo group, pooling of patients assigned to placebo treatment within each cohort is considered for analysis.

For Intent-to-treat (ITT) set, patients will be assigned to either “CT-P59 20 mg/kg”, “CT-P59 40 mg/kg”, “CT-P59 80 mg/kg” or placebo treatment group according to the treatment they were randomized to. The PK and Safety sets will be analyzed according to actual treatment group. Patients receiving at least one kit of CT-P59 will be assigned to the actual treatment group of CT-P59 of corresponding cohort, even if the patient is randomized to placebo group.

The number and percentage of patients in all sets will be tabulated by the treatment group on ITT set. A listing will also be produced displaying data on ITT set.

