12. SAFETY ANALYSES

All Safety analyses will be conducted on the Safety set unless otherwise stated.

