12.11. Antibody-dependent Enhancement

A patient will be considered to have suspicious Antibody-dependent Enhancement (ADE) if it is checked as “Yes” to “Has the subject experienced any suspicious Antibody-dependent Enhancement (ADE) during the study?” on eCRF.

If a patient has suspicious ADE, additional evaluations will be performed as specified in [Appendix 2](#) during the Treatment Period, EOT, and Follow-Up Period. If symptoms have not resolved or have worsened up to Day 7 after the day of suspicious ADE occurrence, same procedure will be repeated until when the symptoms are resolved and/or no SARS-CoV-2 infection is confirmed by RT-PCT (local).

Proportion of patients with suspicious ADE will be summarized by treatment group.

Additional evaluation results will be listed in each evaluation listing. Only ADE Yes/No data will be listed for each patient by treatment group, separately.

13. Changes in the Planned Analysis

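### The first-report table for suspicious ADE, a primary safety endpoint, is labelled ITT, while its own listing and the other safety tables use the Safety set

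*SAP*

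**What the plan says.** Protocol section 2.2.1 lists potential effects on the incidence of ADE among the primary endpoints, analysed on data up to Day 14 of the last enrolled patient.

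On the analysis set, the protocol gives a general rule in section 7.4.3: "Safety analyses will be performed in the Safety Set, unless otherwise indicated". Its ADE subsection, 7.4.3.8, names no set: "The number and percentage of patients with suspicious ADE will be presented by the cohort of CT-P59 groups and pooling of placebo group". The SAP has the same structure. Section 12 says "All Safety analyses will be conducted on the Safety set unless otherwise stated", and section 12.11 says only "Proportion of patients with suspicious ADE will be summarized by treatment group".

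Appendix 5 of the SAP lists the outputs for the first clinical study report and names a set for each. The row for Table 14.3.6.10 has the title "Proportion of patients with Suspicious Antibody-dependent Enhancement" and names the ITT set. Listing 16.2.9.9, which covers the same ADE data, is on the Safety set. So are the other 14.3.x tables in that appendix: 14.3.1.1, 14.3.1.2, 14.3.1.4, 14.3.1.5 and 14.3.6.7.

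SAP section 13.1 records two changes from the protocol, the baseline for clinical recovery and the removal of cell culture. Neither concerns ADE.

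**The concern.** The two sets differ in who is counted and where they are counted. Under SAP sections 5.4.1 and 5.4.2, the ITT set keeps every randomised patient, dosed or not, while the Safety set keeps only those who received study drug. Under SAP section 5.4, the ITT set is grouped by randomised treatment and the Safety set by treatment received: "Patients receiving at least one kit of CT-P59 will be assigned to the actual treatment group of CT-P59 of corresponding cohort", even if that patient was randomised to placebo.

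The plan foresees both situations in which this matters. A patient who is randomised but never dosed can be replaced (protocol section 4.4.1, SAP section 5.3). Receiving a treatment other than the one assigned is the first major deviation named in SAP section 5.6.

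With five patients per CT-P59 cohort and three on pooled placebo, one such patient visibly moves the reported percentage for a primary safety endpoint, and the table would then disagree with its own listing. SAP section 5.4 also has the analysis set shown as a subtitle on each output, so the label would be carried into the report.

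**Working it through.** **Step 1. The places side by side.**

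| Place | Set for suspicious ADE |
|---|---|
| Protocol 7.4.3 (default) and 7.4.3.8 (no set named) | Safety, by default |
| SAP 12 (default) and 12.11 (no set named) | Safety, by default |
| SAP Appendix 5, Listing 16.2.9.9 | Safety, stated |
| SAP Appendix 5, five other 14.3.x tables | Safety, stated |
| SAP Appendix 5, Table 14.3.6.10 | ITT, stated |
| SAP 13.1 (changes from protocol) | ADE not mentioned |

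The table is the only one of these that departs from the Safety set, and no reason is given.

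**Step 2. Inputs.** Each cohort has 5 patients on CT-P59 and 1 on placebo, and there are 3 cohorts (SAP 4.1). The total is 3 × 6 = 18, which agrees with the plan. Placebo is pooled (SAP 5.4), so the planned denominators are 5, 5, 5 and 3. No hypothesis test is planned (SAP 5.2), so there is no power or alpha figure to reproduce.

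**Step 3. Undosed and replaced patients.** The documents give no expected number, so 0 to 2 in a group is assumed, none of them a case. One case gives 1/n, with n the Safety-set size or the ITT size (Safety size plus undosed). For zero cases, the exact one-sided 95% upper limit is 1 − 0.05^(1/n). The plan does not call for this limit; it is shown only to indicate how much reassurance a zero would carry.

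| Group | Undosed | Safety n | ITT n | One case, Safety | One case, ITT | Zero cases, upper limit: Safety | Zero cases, upper limit: ITT |
|---|---|---|---|---|---|---|---|
| CT-P59 cohort | 0 | 5 | 5 | 20.0% | 20.0% | 45.1% | 45.1% |
| CT-P59 cohort | 1 | 5 | 6 | 20.0% | 16.7% | 45.1% | 39.3% |
| CT-P59 cohort | 2 | 5 | 7 | 20.0% | 14.3% | 45.1% | 34.8% |
| Pooled placebo | 0 | 3 | 3 | 33.3% | 33.3% | 63.2% | 63.2% |
| Pooled placebo | 1 | 3 | 4 | 33.3% | 25.0% | 63.2% | 52.7% |
| Pooled placebo | 2 | 3 | 5 | 33.3% | 20.0% | 63.2% | 45.1% |

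**Step 4. One misdosed patient.** Suppose one placebo-randomised patient receives CT-P59 and has suspicious ADE, and everyone else is dosed as randomised without a case.

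- ITT, as randomised: placebo 1/3 = 33.3%; CT-P59 group of that cohort 0/5.
- Safety, as treated: placebo 0/2; CT-P59 group of that cohort 1/6 = 16.7%.

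Listing 16.2.9.9, on the Safety set, would show this patient under CT-P59 while the table counted the case under placebo.

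**Step 5. No undosed or misdosed patient.** The sets coincide and every percentage is the same.

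**The case against.** The strongest reply is that the Safety set is only a default for ADE. Both default rules allow exceptions and neither ADE section names a set, so the explicit ITT label could be the permitted exception. That reading cannot be excluded, but it is weak: the listing of the same data is on the other set, and sections 12.11 and 13.1 are silent. Appendix 5 also labels Listings 16.2.4.5 and 16.2.4.6 (prior and concomitant medication) ITT, although SAP section 8.1 puts them on the Safety set, which points to labelling slips. For the same reason, a reader should not infer that the protocol forbids an ITT table here.

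The practical effect may well be nil. Patients are randomised and dosed on Day 1, after eligibility has been confirmed. Major deviations are listed by patient and dosed ADE cases are listed individually, so in about 18 patients a misplaced case could be traced. This stands, and it limits the importance of the point. It does not explain why table and listing should differ.

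Three stronger readings are tempting, and the documents do not support them:

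- That the table breaks the as-treated rule of SAP section 5.4. That rule covers the Safety and PK sets; for the ITT set the same section prescribes grouping as randomised. The fault is in the choice of set.
- That ADE can only arise in patients who received the antibody. The table counts suspicious ADE, recorded as a yes/no item (SAP 12.11) and defined by excessive symptom progression or investigator opinion (protocol 6.1.14). Neither criterion requires exposure to CT-P59, so a placebo patient can meet it.
- That this is the only safety table in the trial with the problem. Appendix 5 covers the first report only, and the mock shells are a separate addendum, so the statement holds only for the 14.3.x tables listed there.

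**Conclusion.** The inconsistency is real and minor. Table 14.3.6.10 is on a different set from its own listing, from the other five 14.3.x tables in Appendix 5, and from the default in both documents, with no stated reason.

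Its size depends on events that may not occur. Under the assumption of one undosed, replaced patient, a one-case rate falls by 3.3 percentage points in a CT-P59 cohort (20.0 − 16.7) and by 8.3 points in pooled placebo (33.3 − 25.0). One misdosed placebo patient with suspicious ADE moves the case from a CT-P59 group to placebo. With all patients dosed as randomised the effect is zero. The point deserves correction because the endpoint is primary, the groups are very small, and the plan itself provides for both situations.

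**What to change.** In SAP Appendix 5, change the analysis set of Table 14.3.6.10 from ITT to Safety (as treated), to match Listing 16.2.9.9 and the section 12 default. Check the same label in the mock shells, including any version for the final report.

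If ITT was intended, say so and give the reason in SAP section 12.11, record it in section 13.1, and keep the Safety-set table alongside it.

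The cost is one cell, or two short statements and one additional table. No new data are needed. SAP section 5 allows an update after the Data Review Meeting and before hard lock; the change should be made before the lock of the Day 14 data, because the randomisation code is broken after that.
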